15.2. SECONDARY EFFICACY

The secondary efficacy analyses will be performed for the FAS.

15.2.1. SECONDARY EFFICACY VARIABLES & DERIVATIONS

15.2.1.1. Change from baseline in trough FEV₁ on Day 4 (mean of 11 and 12 hour values after evening dose on Day 3) (Secondary variable 1)

Morning trough FEV₁ is defined as mean of values 11 and 12 hours after the evening dose of RPL554 on Day 3.

15.2.1.2. Determination of AUC_{0-4h} FEV₁ (Average FEV₁ over 4 hours) after morning dosing on Day 3 (Secondary variable 2)

Average FEV_1 after morning dosing on Day 3 is defined as the $AUC_{0-4h}FEV_1$ collected during Day 3 under analysis, divided by the length of the time (in hours). $AUC_{0-4h}FEV_1$ is derived using the following formula:

$$AUC = \frac{1}{2}(t_1 - t_0)(y_1 + y_0) + \frac{1}{2}(t_2 - t_1)(y_2 + y_1) + \cdots$$

Where i are the number of intervals, t_i are the time values or time intervals (in actual hours) between assessments and y_i the FEV₁ values. The AUC result will then be divided by the actual time (the time elapsed since morning dosing on Day 3, until the time of assessment) at 4-hour assessment (as this can occur \pm 10 minutes) to obtain the average FEV₁. For analysis purposes, it will be assumed that the pre-dose value occurred at time 0 when computing pharmacodynamic parameters.

If a patient misses' hours 2 and 4 then the AUC₀₋₄ is set to missing.

Document: Z:\RPL554\UYA25849\Biostatistics\Documentation\SAP\Verona RPL554-CO-204 SAP v1.0

Author: [name] Version Number: 1.0

Version Date: [18OCT2018]

Template No.: CS_TP_BS016 Revision 5 Reference: CS_WI_BS005

Effective Date: 01Apr2018

Page 30 of 50

15.2.1.3. Peak FEV₁ (measured in first 4 hours after dosing) and AUC_{0-12h} FEV₁ after dosing on Day 1 (Secondary variable 3)

Peak FEV₁ (after 4 hours of dosing) on Day 1 is defined as the change from baseline to peak FEV₁ and derived similarly to primary analysis (see section 15.1.3), but instead at Day 1.

 $AUC_{0-12h}FEV_1$ on Day 1 is also defined and derived similarly to secondary endpoint above (see section 15.2.1.2), but at Day 1. Parameters will be calculated over 12 hours (on Day 1 of each treatment period). If patient misses hours 8 and 12 then the AUC_{0-12h} is set to missing.

15.2.1.4. Change from baseline in AUC_{0-8h}, AUC_{0-12h} FEV₁ measured on Day 3 (Secondary variable 4)

AUC_{0-8h} and AUC_{0-12h} FEV₁ on Day 3 is defined and derived similarly to secondary endpoint in section 15.2.1.2, but at Day 3. Parameters will be calculated over 8 and 12 hours (on Day 3 of each treatment period), respectively. If patient misses hours 4 and 8 then AUC_{0-8h} is set to missing. Similarly, if 8 and 12 then the AUC_{0-12h} is set to missing.

15.2.1.5. Change from baseline in peak FEV_1 after evening dose on Day 3 (peak over 4 hours) (Secondary variable 5)

Peak FEV₁ on Day 3 evening is defined as the maximum value among the 13, 14 and 16-hour assessments collected after pre-evening dose of each treatment period.

Change from baseline to peak FEV_1 on Day 3 evening (over 4 hours) will be derived to test the hypothesis described in section 15.1.3.

Document: Z:\RPL554\UYA25849\Biostatistics\Documentation\SAP\Verona RPL554-CO-204 SAP v1.0

Author: [name] Version Number: 1.0

Version Date: [18OCT2018]

Template No.: CS_TP_BS016 Revision 5 Reference: CS_WI_BS005

Effective Date: 01Apr2018

Page 31 of 50

15.2.1.6. Determination of onset of action (>10% increase in FEV₁, from pre-first dose, censored at 120 minutes) on Day 1 (Secondary variable 6)

Onset of action is defined as a >10% increase in FEV_1 from pre-dose on Day 1 over the next 120 minutes (2 hours) after morning dosing on Day 1 (5, 15 and 30 minutes and 1, 1.5, 2 hours). Time to onset will be derived as the time to onset of action is achieved. For analysis purposes, it will be assumed that the pre-dose value occurred at time 0. Patients not experiencing an onset of action will be censored at 120 minutes (2 hours) or at time of premature discontinuation (if withdrawn before 120 minutes). If onset of action is deemed to be low (number of patients with onset of action < 10%), the Kaplan-Meier estimates and accompanying figure will not be presented, similar to rescue medications.

15.2.1.7. RV (Residual volume), FRC (Functional residual capacity) and sG_{aw} (Specific airway conductance) at 1.25 hours on Day 1 and 1.25, 8.25 and 12.25 hours after dosing on Day 3 (Secondary variable 7)

RV, FRC, sG_{aw} (1.25 hours) on Day 1 are defined as the lung volume/specific airway conductance assessments recorded pre-dose and 1.25 hours post-dose (on Day 1 of each treatment period). Similarly, RV, FRC, sG_{aw} (pre-dose, 1.25, 8.25 and 12.25 hours) on Day 3 are defined as the lung volume/specific airway conductance assessments recorded pre-dose and 1.25, 8.25 and 12.25 hours, respectively post-dose (on Day 3 of each treatment period).

Document: Z:\RPL554\UYA25849\Biostatistics\Documentation\SAP\Verona RPL554-CO-204 SAP v1.0

Author: [name] Version Number: 1.0

Version Date: [18OCT2018]

Template No.: CS_TP_BS016 Revision 5 Reference: CS_WI_BS005

Effective Date: 01Apr2018

Page 32 of 50

15.2.1.8. RPL554 steady state pharmacokinetics (AUC_{0-12h}, Cmax, time to maximum concentration [tmax]) (Secondary variable 8)

Concentration of RPL554 (AUC_{0-12h}, C_{max} [maximum concentration], t_{max} [time to maximum concentration]) on Day 3 of each treatment period (pre-dose, 5, 30 and 45 minutes and 1, 1.5, 2, 4, 8 and 12-hours post dose).

15.2.2. MISSING DATA METHODS FOR SECONDARY EFFICACY VARIABLE(S)

Missing data will not be imputed similarly to primary endpoint, where applicable (see section 15.1.2).

15.2.3. ANALYSIS OF SECONDARY EFFICACY VARIABLES

15.2.3.1. Analysis of Secondary Variables 1, 2, 3, 4, 5 and 7

The secondary endpoints listed above will be analyzed in the same way as the primary endpoint. In the analyses using AUC of the FEV_1 , the average FEV_1 at the each timepoint of interest will be used. Similarly, to the primary analysis, average AUC of the FEV_1 and baseline FEV_1 will be log-transformed prior to analysis using natural logarithm and the difference between the two will be estimated, with log (baseline FEV_1), being a covariate.

In the analysis of the RV, FRC and sG_{aw} the pre-dose will be used as baseline in the model and the dependent endpoint will be the change at each timepoint of interest (1.25 hours after dosing on Day 1 and 1.25, 8.25 and 12.25 hours after dosing on Day 3).

15.2.3.2. Analysis of Secondary Variable 6

Onset of action will be summarized by treatment and a Kaplan-Meier plot illustrating time to onset constructed. The SAS® procedure LIFETEST including covariates, if relevant, will be used as follows:

Document: Z:\RPL554\UYA25849\Biostatistics\Documentation\SAP\Verona RPL554-CO-204 SAP v1.0

Author: [name] Version Number: 1.0

Version Date: [18OCT2018]

Template No.: CS_TP_BS016 Revision 5 Reference: CS_WI_BS005

Effective Date: 01Apr2018

Page 33 of 50

```
PROC LIFETEST DATA=... OUTSURV =... CONFTYPE = LINEAR METHOD =

KM ALPHA = 0.05 ALPHAQT = 0.05 PLOTS = (SURVIVAL (FAILURE NOCENSOR));

TIME ONSET*STATUS (1);

STRATA TRT;

RUN;

where ONSET = time to onset of action

TRT = treatment group

STATUS (1) = indicates an event of onset of action
```

If a patient does not have onset of action from pre-dose on Day 1 over the next 120 minutes (2 hours) the data will be censored at 120 minutes or if a patient prematurely discontinued before 120 minutes, the last available assessment time post-dose (1 indicates censored variables).

15.2.3.3. Analysis of Secondary Variable 8

Summary statistics (number of observations, geometric mean, CV [coefficient of variation], minimum and maximum) will be presented for the concentrations of RPL554, specifically AUC_{0-12h} , C_{max} and t_{max} on the PK analysis set population.

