9.4.5 Efficacy/Pharmacodynamics

FEV₁ and FVC will be summarized as actual and change from baseline using descriptive statistics over time.

The peak effect on FEV_1 during these time intervals will be computed as the maximum value in the 4 hours after dosing. The average effect will be calculated as the AUC divided by the length of the time interval of interest. For analysis, the peak, average and trough FEV_1 will be divided by the pre-dose Day 1 baseline value.

Computed pharmacodynamic parameters for FEV_1 will be compared between the three study treatments using analysis of covariance (ANCOVA) models with fixed factors for treatment, period and patient, and using the pre-dose Day 1 baseline value as a covariate. FEV_1 will be analyzed using multiplicative models, which means that data (dependent and baseline) are logged prior to analysis and the result then transformed back to the linear scale giving treatment differences as ratios of geometric means.

Primarily the combination RPL554+tiotropium/olodaterol will be compared to tiotropium/olodaterol alone for each of the two doses of RPL554. Results of the comparisons will be expressed as the mean geometric ratio with 95% confidence intervals and associated, 2-sided, p-value.

Onset of action will be summarized by treatment and a Kaplan-Meier plot illustrating time to onset constructed.

Outcomes from the whole body plethysmography at 1.25 hours post-dose on Day 1 and 1.25, 8.25 and 12.25 hours post-dose on Day 3 will be compared in the same way as FEV₁ using multiplicative ANOVA models. The baseline of the visit (pre-first dose in a treatment period) will be used as covariate in these models.

The use of rescue medication during the study visits will be summarized by treatment, and, if appropriate, a Kaplan-Meier plot illustrating time to first use of rescue constructed.

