3. STUDY DESIGN

3.1. GENERAL DESCRIPTION

This is a Phase II, randomized, double blind, placebo controlled, complete block three-way crossover study to

Document: Z:\RPL554\UYA25849\Biostatistics\Documentation\SAP\Verona RPL554-CO-204 SAP v1.0

Author: [name] Version Number: 1.0

Version Date: [18OCT2018]

Template No.: CS_TP_BS016 Revision 5 Reference: CS_WI_BS005

Effective Date: 01Apr2018

Page 11 of 50

investigate treatment with nebulized RPL554 and tiotropium/olodaterol Respirat® in patients with moderate to severe chronic obstructive pulmonary disease (COPD).

A total of approximately 70 male or female COPD patients (as defined by the American Thoracic Society [ATS]/European Respiratory Society [ERS] guidelines with symptoms compatible with COPD for at least 1 year prior to Screening) aged 40 to 80 years (inclusive) will be randomized across up to 4 sites, in the Unites States (US) and the United Kingdom (UK). All patients will receive 3 combinations of study treatment (1.5 mg RPL554, 6 mg RPL554 and placebo) in a randomized, crossover design; therefore, each patient will act as his or her own control in the study. There are 6 possible treatment sequences a patient can be randomized to: a) RPL544 1.5 mg / RPL544 6.0 mg/Placebo, b) RPL544 1.5 mg / Placebo / RPL544 6.0 mg, c) RPL544 6.0 mg / RPL544 1.5 mg / Placebo, d) RPL544 6.0 mg / RPL544 1.5 mg, e) Placebo / RPL544 1.5 mg / RPL544 6.0 mg and f) Placebo / RPL544 6.0 mg / RPL544 1.5 mg, with the ratio of patients to treatment groups / treatment sequences being 1:1:1:1:1:1.

Patients will be screened for eligibility, including a reversibility test with salbutamol (in UK) or albuterol (in US) and ipratropium between 7 and 14 days before the first dose of study treatment. Eligible patients will then attend 3 separate treatment periods (Treatment periods 1 to 3), with each lasting 3 days and separated by a 7 to 14-day washout period. Figure 1 below summarizes these details.

Document: Z:\RPL554\UYA25849\Biostatistics\Documentation\SAP\Verona RPL554-CO-204 SAP v1.0

Author: [name] Version Number: 1.0

[figure not shown]
Version Date: [18OCT2018]

Template No.: CS_TP_BS016 Revision 5 Reference: CS_WI_BS005

Effective Date: 01Apr2018

Figure 1 Study Flow Chart

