6.5. STATISTICAL TESTS

The default significant level will be (5%); confidence intervals will be 95% and all tests will be 2-sided, unless otherwise specified in the description of the analyses. All significant p-values (i.e. < 0.05) will be flagged by means of an "*" for ease of review.

For presentation of summary statistics for quantitative and qualitative variables see Appendix 1; Programming conventions for outputs.

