7.4. MULTIPLE COMPARISONS/ MULTIPLICITY

Significance of treatment effect will be tested for the primary and secondary efficacy endpoints and will be done for each of the 2 doses of RPL554 against placebo, starting with the highest dose (6 mg). To this end, the fixed-sequence testing approach (Maurer et al., 1995; Westfall & Krishen, 2001) will be used.

Let i = 0, 1 and 2 represent increasing dose levels, 0 denoting placebo. Also, let μ_i , i = 0, 1 and 2, denote the mean change from baseline in peak FEV₁ at Day 3 (measured in first 4 hours after morning dosing) for placebo and each increasing active dose level, respectively. The primary null hypotheses are defined as:

H_i: $\mu_i - \mu_0 = 0$ and will be tested against the 2-sided alternative K_i: $\mu_i - \mu_0 \neq 0$, i = 1 and 2

Document: Z:\RPL554\UYA25849\Biostatistics\Documentation\SAP\Verona RPL554-CO-204 SAP v1.0

Author: [name] Version Number: 1.0

Version Date: [18OCT2018]

Template No.: CS_TP_BS016 Revision 5 Reference: CS_WI_BS005

Effective Date: 01Apr2018

Page 20 of 50

Finally, let p_1 and p_2 denote the marginal p-values obtained from the statistical tests associated with H_1 and H_2 (obtained from the model).

The fixed-sequence testing will begin with the null hypothesis corresponding to the highest dose versus placebo. If a statistically significant difference is found at the 2-sided α level of 5%, the testing will proceed with the next highest dose. Otherwise, testing stops and the remaining null hypotheses are accepted without testing.

This testing strategy can be written as the following stepwise algorithm:

- Step 1: If $p_2 \le \alpha$ reject H_2 and go to Step 2. Otherwise, fail to reject H_2 and H_1 and stop.
- Step 2: If $p_1 \le \alpha$ reject H_1 . Otherwise, accept H_1 .

The fixed-sequence procedure controls the family-wise error rate in the strong sense because, for each null hypothesis, the testing is conditional upon rejecting all hypotheses earlier in the sequence (Dmitrienko, et al., 2009).

Each secondary endpoint will be tested independently and nominally following a hierarchical testing of doses like the one used for the primary.

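### Onset of action: SAP 7.4 promises a test of each dose against placebo, but the code in SAP 15.2.3.2 cannot produce it, and the tests it prints by default ignore the crossover

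*SAP*

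**What the plan says.** **The promise.** SAP 7.4 states: "Significance of treatment effect will be tested for the primary and secondary efficacy endpoints and will be done for each of the 2 doses". The comparator is placebo, and the 6 mg dose comes first. It then adds: "Each secondary endpoint will be tested independently and nominally following a hierarchical testing of doses like the one used for the primary". SAP 6.5 sets the level: "The default significant level will be (5%); confidence intervals will be 95% and all tests will be 2-sided". It also says that significant p-values will be flagged.

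**The status of onset.** It is listed among the secondary efficacy variables ("15.2.1.6. Determination of onset of action", secondary variable 6). The event is a rise in FEV1 of more than 10% from the Day 1 pre-dose value, read at 5, 15, 30, 60, 90 and 120 minutes and censored at 120 minutes.

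**The analysis given.** SAP 15.2.3.1 sends secondary variables 1 to 5 and 7 to the primary mixed model, which has a period term and a random patient effect. Variable 6 is left out. SAP 15.2.3.2 gives it one sentence, "Onset of action will be summarized by treatment and a Kaplan-Meier plot illustrating time to onset constructed", and a PROC LIFETEST call with `STRATA TRT`. The lead-in allows covariates if relevant but names none. Protocol 9.4.5 has the same descriptive wording: "Onset of action will be summarized by treatment and a Kaplan-Meier plot illustrating time to onset".

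**The design.** SAP 3.1 describes a three-way crossover: "therefore, each patient will act as his or her own control in the study".

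**The concern.** A programmer who follows the SAP reaches the onset endpoint with an instruction to test 6 mg and then 1.5 mg against placebo, and with code that does neither. What LIFETEST prints with three strata is an overall 2-degree-of-freedom comparison in three versions (log-rank, Wilcoxon and likelihood ratio). None is a dose-versus-placebo contrast. All take the three onset times of one patient as coming from three unrelated patients, and period is not in the model.

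Onset is a named secondary objective. In the earlier add-on study to tiotropium, Protocol 1.1 reports onset as a comparison (4.2 versus 37 minutes). A similar statement from this trial would have no interval or p-value that respects the design. Because SAP 6.5 flags every significant p-value and nothing excludes the default LIFETEST output, one of those overall tests could be reported in its place.

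**Working it through.** **Step 1: the sections side by side.**

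| Needed for the SAP 7.4 test | Provided in SAP 15.2.3.2 |
|---|---|
| 6 mg vs placebo, then 1.5 mg vs placebo | One overall comparison of three treatments |
| Within-patient comparison (SAP 3.1) | No patient identifier |
| Period adjustment, as in the primary model | No period term |
| An estimate with a 95% interval | Curves and quantiles per treatment; no between-treatment estimate |

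The mismatch follows from the text alone. The next steps only size its effect on the default tests.

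**Step 2: inputs.** From the documents: 70 patients, two-sided 5%, the six reading times, censoring at 120 minutes, and a control median of 37 minutes borrowed from the earlier study. Assumed: exponential onset times and a within-patient correlation ρ (Gaussian copula) between 0 and 0.8. The plan states no power or event count for onset, so there is no figure of its own to reproduce. Its 80% power statement concerns peak FEV1.

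**Step 3: a hand check.** With equal correlation r between a patient's log-rank score contributions, the true variance of every treatment contrast is (1 − r) times what the unpaired test assumes. Under the null the statistic is then (1 − r) times a chi-square on 2 df. Its 5% critical value is −2 ln 0.05 = 5.991, so

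P(reject) = exp(−(5.991/2)/(1 − r)) = 0.05^(1/(1 − r)).

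This gives 0.05^1 = 5.0% at r = 0, 0.05^1.25 = 2.4% at 0.2, 0.05^2 = 0.25% at 0.5, and 0.05^3.33 = 0.005% at 0.7.

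**Step 4: simulation under the null** (5,000 trials per setting; simulation error about √(0.05 × 0.95/5000) = 0.3 points).

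| ρ | Overall log-rank, 3 groups | Patient-clustered log-rank, 6 mg vs placebo |
|---|---|---|
| 0 | 5.3% | 5.5% |
| 0.1 | 3.9% | 5.5% |
| 0.2 | 2.9% | 5.4% |
| 0.3 | 1.6% | 5.2% |
| 0.5 | 0.7% | 5.8% |
| 0.7 | 0.04% | 4.9% |
| 0.8 | 0.0% | 5.3% |

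The overall test is slightly less conservative than the formula at the same nominal value. That is expected, because grouping the times and censoring them weakens the correlation of the scores. With a 10-minute median the overall log-rank rejects 3.0% / 0.8% / 0.0% at ρ = 0.2 / 0.5 / 0.8.

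**Step 5: power** under assumed hazard ratios of 1.5 (6 mg) and 1.3 (1.5 mg) against placebo, 2,000 trials per setting.

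| ρ | Overall, 3 groups | Unpaired, 6 mg vs placebo | Clustered, 6 mg vs placebo |
|---|---|---|---|
| 0 | 53% | 62% | 64% |
| 0.2 | 51% | 62% | 69% |
| 0.5 | 48% | 64% | 85% |
| 0.8 | 45% | 74% | 99% |

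The last two columns are the like-for-like comparison; the overall test answers a different question. The model proposed below was also run with log-onset SD 1.5, a placebo median of 37 minutes and a shift of 0.5 log units, all assumed. Its null rejection rate was 4–6%, and its power was 44% / 50% / 67% / 83% at ρ = 0 / 0.2 / 0.5 / 0.7. In that setting an unpaired two-group log-rank had 43% / 43% / 40% / 41%.

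**Step 6: the status code.** The legend under the code says STATUS(1) marks an onset event. The sentence after it says that 1 means censored. In the TIME statement as printed, the bracketed value is the censored one. If the data were coded by the legend, onsets would be read as censored and the curves would be wrong.

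**The case against.** The strongest reply is that onset is meant to be descriptive. Neither SAP 15.2.3.2 nor Protocol 9.4.5 names a log-rank, a hazard ratio or a p-value, and the LIFETEST options serve curves and quantiles. SAP 7.4 writes its hypotheses as mean changes in peak FEV1, with p-values from the model, and onset has no such model. The onset objective does not mention placebo, whereas several others do.

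Much of this stands. A reader might infer that the plan sets out to compare treatments with an unpaired log-rank. It does not: those tests are default software output, not a stated analysis. But the descriptive reading does not remove the conflict. SAP 7.4 covers secondary endpoints without exception. The wording of the objective does not settle the matter either, since the evening-peak and lung-volume objectives also omit placebo and yet go to the primary model. On either reading one of the two SAP sections has to change.

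Three other inferences go too far:

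- **The tests are severely conservative.** That depends on a correlation the documents do not give. At 0 to 0.1 the rejection rate is close to nominal (5.3%, 3.9%).
- **The power loss is bound to matter.** For an effect as large as in the earlier study, ln(37/4.2) = 2.18 log units, an unpaired two-group log-rank reached 100% power in simulation at correlations of 0 to 0.7. The background there was tiotropium alone, so the effect here may be smaller.
- **Every patient supplies three onset times.** That is the design intent, but the full analysis set admits patients with two periods.

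**Conclusion.** The point holds as an inconsistency within the SAP. Section 7.4 promises ordered dose-versus-placebo tests for onset, and section 15.2.3.2 cannot deliver them. This rests on the text and needs no assumption.

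The second part is conditional. If onset times are positively correlated within patient, the homogeneity tests that LIFETEST prints are conservative, increasingly so as the correlation rises: about 5% / 3% / 0.7% / 0% true rejection at nominal 5% for assumed correlations of 0 / 0.2 / 0.5 / 0.7.

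A reader might infer that the Kaplan-Meier results are invalid or that false claims of faster onset become more likely. Neither follows. Each patient contributes at most one time to each treatment's curve, so the curves and medians are sound, provided 1 is coded as censored. For positive correlation the error lies towards missing a difference. The consequence is lost power and a missing treatment estimate on a nominally tested secondary endpoint; the primary analysis is unaffected. The SAP should be corrected before unblinding.

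**What to change.** Choose one of two routes and write it into SAP 7.4 and 15.2.3.2.

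1. **If onset is to be tested.** Keep the Kaplan-Meier curves as description. Add a Cox model with TREATMENT and PERIOD and patient-clustered robust variance: PROC PHREG with `COVS(AGGREGATE)` and `ID USUBJID`, placebo as reference. Use Efron or Breslow ties, not discrete, so that tie handling is compatible with the robust variance. Report 6 mg and then 1.5 mg against placebo as hazard ratios with 95% intervals, in the 7.4 order. Do not report the p-values that `STRATA TRT` prints.
2. **If onset is descriptive only, as Protocol 9.4.5 suggests.** Exempt secondary variable 6 from 7.4 by name and suppress the LIFETEST tests.

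On either route, correct the legend so that STATUS = 1 means censored throughout.

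The cost is one SAP paragraph and a few lines of SAS. No new data are needed.

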9.4.6 Pharmacokinetics

The following steady state pharmacokinetic parameters will be calculated from plasma concentrations of RPL554 using standard non-compartmental methods.

- AUC_{0-12h} represents the area under the plasma concentration curve from time 0 to 12 hours after dose on Day 3. The AUC_{0-12h} value in indicative of the steady state AUC_T for a twice daily dosage regimen of RPL554 for the study cohort
- C_{max} denotes the highest plasma concentration measured
- t_{max} denotes the time point corresponding to C_{max}

Pharmacokinetic parameters will be summarized by dose level using descriptive statistics (n, geometric mean, coefficient of variation (CV), minimum, maximum and median for AUC parameters, C_{max} , n, arithmetic mean, standard deviation, minimum, maximum and median for t_{max}).

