3.3. CHANGES TO ANALYSIS FROM PROTOCOL

Not applicable.

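### SAP 15.2.3.3 summarises tmax by geometric mean and CV and drops the median for all three PK parameters, contrary to protocol 9.4.6 and with no change declared

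*SAP*

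**What the plan says.** Protocol 9.4.6 sets the grouping first: "Pharmacokinetic parameters will be summarized by dose level using descriptive statistics". It then gives two lists. The first is n with "geometric mean, coefficient of variation (CV), minimum, maximum and median for AUC parameters", and it also covers Cmax. The second, for tmax, reads "n, arithmetic mean, standard deviation, minimum, maximum and median for" tmax.

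SAP 15.2.3.3 has a single sentence. Its statistics are the number of observations and "geometric mean, CV [coefficient of variation], minimum and maximum", to be given for RPL554 concentrations, which it then specifies as AUC0-12h, Cmax and tmax, "on the PK analysis set population". There is no separate list for tmax.

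Two other SAP sections bear on this. Section 4.3 says that an outside vendor performs the PK analysis but that the SAP will give its details. Section 3.3, the place for changes from the protocol's analysis, reads "Not applicable".

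**The concern.** Steady-state PK (AUC, Cmax, tmax) is a listed secondary endpoint in protocol 9.3.2. The two documents prescribe different statistics for it, and the SAP says nothing has changed. Because an outside party will work from the SAP text, the written list is likely to be what is produced.

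For AUC and Cmax the loss is only the median. For tmax the summary moves from the arithmetic to the log scale, which fits the variable badly. tmax is the sampling time at which the highest concentration was seen, so it falls on a coarse grid, and that grid includes a sample taken before the dose. A log-scale summary gives extra weight to the earliest times and cannot handle a time of zero. At stake is whether the study report describes time to peak in the way the protocol promised and in a form that can always be computed.

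**Working it through.** The plan gives no figure to reproduce. The check is a comparison of the two texts, followed by a small illustration.

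**Step 1. The lists side by side**

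| Parameter | Protocol 9.4.6 | SAP 15.2.3.3 | Difference |
|---|---|---|---|
| AUC0-12h, Cmax | n, geometric mean, CV, minimum, maximum, median | n, geometric mean, CV, minimum, maximum | median lost |
| tmax | n, arithmetic mean, SD, minimum, maximum, median | n, geometric mean, CV, minimum, maximum | arithmetic mean, SD and median lost; geometric mean and CV put in their place |
| Grouping | by dose level | only the analysis set is named | SAP 15.2.3.3 silent |
| Change declared (SAP 3.3) | – | none | undeclared |

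**Step 2. What values tmax can take**

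Protocol 7.3 and SAP 15.2.1.8 give the Day 3 sampling times: pre-dose, 5, 30 and 45 minutes, and 1, 1.5, 2, 4, 8 and 12 hours. Protocol 9.4.6 defines Cmax as the highest measured concentration and tmax as its time point. Neither document excludes the pre-dose sample, which on Day 3 follows earlier twice-daily doses. Protocol 5.4.2.1 sets time 0 at the end of nebulization, so the pre-dose sample lies before time 0. No rule says how a pre-dose tmax is to be coded.

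**Step 3. How the statistics behave on that grid**

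The data here are assumed, for illustration only; the documents give no tmax distribution. Take ten patients, nine with tmax at 60 minutes and one at 5 minutes.

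- Median: 60 minutes.
- Arithmetic mean: (9 × 60 + 5) / 10 = 54.5 minutes.
- Geometric mean: 60 × (5/60)^(1/10) = 60 × 0.78 = about 47 minutes.

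One early value in ten moves the geometric mean about 13 minutes below the median and the arithmetic mean 5.5 minutes below it.

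Now let the tenth patient have a pre-dose maximum coded as 0.

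- Median: 60 minutes.
- Arithmetic mean: 540 / 10 = 54 minutes.
- Geometric mean: the product contains a zero, so it is 0; computed through logarithms it is undefined, because log(0) does not exist.

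The protocol's statistics can be calculated in both cases. The SAP's geometric mean fails in the second.

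**The case against.** The case for leaving the text alone has several parts.

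- **The tmax = 0 case is hypothetical.** It needs a pre-dose trough above every later sample, and a coding rule that sets it to 0. Nothing in the documents says this is expected. That stands, so it is a weakness of the chosen statistic and not a predicted failure. It would also be too strong to say that 5-minute values dominate the geometric mean: with one such value in ten they pull it down and no more. Minimum and maximum remain in the SAP list.
- **Appendix 1 already includes the mean, SD and median.** It does, but as a general order of presentation across tables. The explicit PK list in 15.2.3.3 is the specific text and would normally prevail.
- **The vendor does the PK work.** This is no defence, since SAP 4.3 places the details in the SAP.
- **The table templates may supply the rest.** SAP section 8 refers to templates that set format and content. They are not available here, so this cannot be ruled out; it does not remove the conflict between the two texts.
- **Protocol version.** SAP section 1 cites protocol version 2.0 of 10 July 2018, whereas the supplied protocol describes itself as the first version. Whether 9.4.6 differs elsewhere cannot be checked. This stands as a limit.

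A reader might also infer from the missing dose-level wording that the SAP will pool 1.5 mg and 6 mg, which would make the AUC and Cmax summaries uninterpretable. The documents do not support that. Section 15.2.3.3 is silent on grouping, but Appendix 1 sets separate output groups for RPL554 1.5 mg and 6.0 mg, and says that totals across treatment groups are in general shown only at baseline or randomization. No passage plans a pooled summary.

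**Conclusion.** The point holds in a limited form. On the supplied texts, SAP 15.2.3.3 contradicts protocol 9.4.6 for tmax, omits the median for AUC0-12h, Cmax and tmax, and leaves the change undeclared in SAP 3.3. For tmax the substitution is also a poor choice, because the variable is discrete and the geometric mean breaks down at zero. The absent dose-level wording is a gap in clarity, not a second contradiction.

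The size is small. Only descriptive reporting of one secondary endpoint changes. The primary comparison, the alpha and the power are untouched, and the individual values would allow any summary to be produced later. The conclusion assumes that section 9.4.6 reads the same in the protocol version the SAP follows, and that the templates do not already restore the missing statistics.

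**What to change.** In SAP 15.2.3.3, replace the single list with two:

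- AUC0-12h and Cmax: n, geometric mean, CV, median, minimum, maximum.
- tmax: n, arithmetic mean, SD, median, minimum, maximum.

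Adding that both are presented by dose level is optional; it would put in words what Appendix 1 already points to. If the sponsor prefers the present list, the change should instead be declared and justified in SAP 3.3.

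The cost is about one sentence of SAP text. No new data are needed and no other analysis is affected.
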